6.8.1 Dose modifications due to hematologic toxicity

Complete blood counts (CBC) will be obtained for all patients at the beginning of each treatment cycle (Day 1). If hematologic toxicity occurs, treatment should be held and ANC and platelets should be monitored weekly (or more often as clinically indicated) until recovery.

Table 7 Day 1 Haematologic Dose Modifications and Management

Treatment Day Blood Counts and Toxicity			
ANC		Platelets	Action
≥1000/μL	And	≥75,000/μL	No dose modification or interruption
<1000/μL	Or	<75,000/μL	Delay by 1 week intervals until recovery

If haematologic parameters do not recover within 21 days, the patient should be removed from the study treatment.

Table 8 Neutropenia, Infection, Febrile Neutropenia Dose Modifications and Management

Any Day	
Grade 3 neutropenic fever (ANC <1000/ μ L + Temperature \geq 101°F [38.5°C]) or neutropenic infection Documented infection with Grade 3 neutropenia (ANC <1000/ μ L) Grade 4 neutropenia (ANC <500/ μ L >7 days) Grade 4 thrombocytopenia (platelet count <25,000/ μ L >7 days)	Hold dose until recovery. Then, upon resuming dosing, reduce AZD1775 to the next lower dose level^a.
Grade 4 febrile neutropenia or Grade 4 infection with neutropenia (both defined as septic shock) Thrombocytopenic haemorrhage (gross occult bleeding) associated with a platelet count <50,000/ μ L	Discontinue treatment and follow for disease progression.

a No more than two dose reductions will be allowed for any patient. Patients requiring additional dose modifications due to toxicity will discontinue study treatment.

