This Clinical Study Protocol has been subject to a peer review according to AstraZeneca Standard procedures. The clinical study protocol is publicly registered and the results are disclosed and/or published according to the AstraZeneca Global Policy on Bioethics and in compliance with prevailing laws and regulations.

PROTOCOL SYNOPSIS

A Phase Ib, Open-Label, Multi-Centre Study to Assess the Safety, Tolerability, Pharmacokinetics, and Anti-tumour Activity of AZD1775 Monotherapy in Patients with Advanced Solid Tumours

Principal Investigator

Study site(s) and number of patients planned

Approximately 172 total patients will be treated at approximately 20 investigational sites in the United States and Canada.

Study period		Phase of development
Estimated date of first patient enrolled	Q2 2015	1
Estimated date of last patient completed	Q1 2018	1

Study design

This open-label, multi-centre, Phase Ib study is designed to evaluate the safety, tolerability, pharmacokinetics, and anti-tumour activity of oral AZD1775 monotherapy. The study is divided into two parts: Part A safety lead-in cohort of patients with advanced solid tumours, and Part B expansion cohorts in which patients will be organised by tumour type and molecular profile to evaluate anti-tumour activity. Initially, a retrospective molecular analysis of tumour samples may be performed on approximately the first 15 patients under each tumour type. These patients will be allocated to the biomarker-negative or positive cohort retrospectively, once their genetic profile analysis result is available from the central lab. To ensure balance between the biomarker-positive and biomarker-negative cohorts, a switch to prospective molecular analysis at study entry will be required as patient enrolment advances after this point. A quality check of the submitted pathology material will be performed for both groups pre-treatment.

Treatment with AZD1775 monotherapy may continue until disease progression, unacceptable toxicity, or other discontinuation criteria has occurred as described in Section 3.9. Alternative dosing regimens and schedules may be studied depending on toxicities and emerging data.

Part A – safety lead-in cohort (closed to enrollment 2015)

AZD1775 (200 mg BID PO) will be taken in 12 hour intervals over 3 days (Days 1-3) for a total of 6 doses on week 1 and week 2 of each 21-day cycle (see [Figure 2](#)).

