5.2.5 Vital signs

Vital signs to be assessed include: resting heart rate, blood pressure, temperature and weight at the screening visit and at times shown in the study plan. Height will be measured at the screening visit only. Vital signs and weight will be obtained prior to study drug administration according to institutional practice (see Table 1 and Table 2).

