6.8 Dose modifications

Toxicity will be assessed utilizing the NCI CTCAE v4.03 (<http://evs.nci.nih.gov/ftp1/CTCAE/CTCAE>), unless otherwise specified.

The DLT criteria in Section 7.2.1 will be used to assess the safety lead-in cohort during Part A Cycle 1. Toxicity occurring in patients beyond Cycle 1 of the Part A safety lead-in will be graded and the appropriate dose modification or supportive care will be administered to decrease the signs and symptoms thereof according to this section.

The DLT criteria evaluations do not apply to Part B. Dose adjustments will be based on the organ system exhibiting the greatest degree of toxicity. Dose reductions or holds and initiation of supportive care are allowed as clinically indicated by the treating physician. A maximum of 2 dose reductions for the AZD1775 will be allowed. Patients requiring >2 dose reductions will be discontinued from the study drug. Dose reductions are presented for AZD1775.

Table 6 AZD1775 Dose Level Reductions for Toxicity

Dose Level	AZD1775 ^a	Schedule 21-day cycle
Starting Dose ^b	175 mg PO BID	Days 1-3 and 8-10
Dose Level -1	150 mg PO BID	Days 1-3 and 8-10
Dose Level -2	125 mg PO BID	Days 1-3 and 8-10

^a AZD1775 taken in 12 hour intervals

^b **Note:** the AZD1775 starting dose is reduced to 175 mg BID because 200 mg BID was not well-tolerated.

Any patient requiring a toxicity-related dose delay of more than 21 days from the intended day of the next scheduled dose must be discontinued from the study unless there is approval from the Medical Monitor for the patient to continue.

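### Table 8 equates 101°F with 38.5°C in the neutropenic-fever trigger; the two differ by 0.17°C, so a mandatory dose reduction can depend on the unit read

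*Protocol*

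**What the plan says.** Table 8 in Protocol Section 6.8.1 applies on any day of treatment. Its first trigger is Grade 3 neutropenic fever, defined as ANC below 1000/µL plus a temperature at or above "101°F [38.5°C]) or neutropenic infection". The action is to hold dosing until recovery and then, on restarting, "reduce AZD1775 to the next lower dose level".

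Three other entries lead to the same action without any temperature: "Documented infection with Grade 3 neutropenia", ANC below 500/µL for more than 7 days, and platelets below 25,000/µL for more than 7 days.

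Section 6.8 limits how often the action can be taken: "A maximum of 2 dose reductions for the AZD1775 will be allowed". A patient who needs more comes off study drug. Table 6 sets the levels at 175, 150 and 125 mg BID.

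Section 5.2.5 includes temperature among the vital signs but names no unit: "Vital signs to be assessed include: resting heart rate, blood pressure, temperature and weight". The Synopsis places the study at "approximately 20 investigational sites in the United States and Canada".

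**The concern.** The trigger gives one threshold in two units, and the two figures are not conversions of each other. A site working in Fahrenheit and a site working in Celsius can each follow the table in good faith and apply different rules.

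Two things are at stake. The first is whether a given patient must lose a dose level and use one of the two reductions allowed. The second is whether a site that did not reduce a patient at, say, 38.4°C deviated from the protocol. Dose reductions and dose intensity are summarised as exposure data (Sections 8.3.2 and 8.7.1), so any inconsistency also passes into those tables.

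**Working it through.** **Inputs.** Both temperatures come from Table 8 (Section 6.8.1). The dose levels come from Table 6 (Section 6.8).

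**Does the bracketed figure reproduce?** With C = (F − 32) × 5/9 and F = C × 9/5 + 32:

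- 101°F: (101 − 32) × 5/9 = 38.33°C. Table 8 prints 38.5°C, so its figure is not reproduced.
- 38.5°C: 38.5 × 9/5 + 32 = 101.3°F. Table 8 prints 101°F.
- Gap: 38.5 − 38.33 = 0.17°C, or 101.3 − 101 = 0.3°F.

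**Could rounding explain it?** To one decimal, 101°F is 38.3°C, not 38.5°C. In the other direction, 101.3°F becomes 101°F if rounded to a whole degree. That may be how the figure arose, but it does not make the two cut-offs agree for thermometers read to one decimal.

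**Which readings are classified differently?**

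| Reading (°F) | °C | Meets ≥101°F | Meets ≥38.5°C |
|---|---|---|---|
| 100.9 | 38.28 | no | no |
| 101.0 | 38.33 | yes | no |
| 101.1 | 38.39 | yes | no |
| 101.2 | 38.44 | yes | no |
| 101.3 | 38.50 | yes | yes |

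The disagreement runs from 38.33°C up to, but not including, 38.5°C.

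**Does another part of the protocol settle which figure governs?** No. Section 5.2.5 fixes no unit. Section 6.8.3.3 on febrile neutropenia and the DLT criteria in Section 7.2.1 give no temperature. Section 6.8 uses CTCAE v4.03 only where nothing else is specified, and Table 8 does specify a temperature.

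**What does the trigger add for a patient in the band?** Section 6.8.1 already calls for a hold when haematologic toxicity occurs, and Table 7 delays treatment when the ANC is below 1000/µL. Neither requires a lower dose on restarting. Meeting the fever trigger turns the hold into a compulsory step down, for example from 175 to 150 mg BID: (175 − 150)/175 = 14% of the dose. The patients for whom the unit decides the matter are therefore those with:

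- ANC below 1000/µL;
- a temperature in the band above; and
- none of the temperature-free triggers in the same table.

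**The case against.** No one disputes the conversion; the case on the other side is about reach.

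- **The hold hardly depends on temperature.** Section 6.8.1 and Table 7 already stop dosing for low counts. This stands: what depends on the unit is essentially the compulsory reduction on restarting.
- **Other triggers catch many of the same patients.** Infection with ANC below 1000/µL and prolonged Grade 4 neutropenia lead to the same action at any temperature. This also stands, and it narrows the affected group further.
- **The physician can act anyway.** Section 6.8 says "Dose reductions or holds and initiation of supportive care are allowed as clinically indicated by the treating physician", and Section 6.8.3.3 governs acute care of the fever without citing the Table 8 temperature. It is true that treatment of the fever does not hinge on the figure. But permission to reduce does not make a compulsory rule consistent, and it does not say whether a site that did not reduce broke the rule.
- **Nothing inferential changes.** Dose reduction and dose intensity are descriptive exposure summaries, not listed primary or secondary outcome measures. The study has no formal hypothesis test, and the DLT criteria contain no temperature. All of this stands.
- **Differing units across sites is an inference.** The protocol does not say which unit any site uses. Because Fahrenheit is printed first, 101°F may be the intended value and the bracket a loose conversion. That reading is plausible, but the text does not state it, and a site reading Celsius would see only 38.5°C as its cut-off.

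These points limit the size of the problem. They do not remove the mismatch.

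**Conclusion.** The concern holds. Table 8 prints two different thresholds as one, and no other part of the protocol chooses between them. The band of disagreement is 0.17°C (0.3°F) wide. Within it, a patient with ANC below 1000/µL and no other Table 8 trigger must drop a dose level under the Fahrenheit figure and need not under the Celsius figure.

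The practical weight is small. Few patients will fall in the band, dosing is generally held for low counts in any case, and the efficacy analyses, the sample size and the DLT rules are untouched. The protocol gives no rate of neutropenic fever, so the number affected cannot be estimated from it.

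The conversion needs no assumptions. The effect on conduct assumes that some sites read temperature in Celsius and others in Fahrenheit, which the protocol leaves open. It is a correction worth making, not a threat to the study's conclusions.

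**What to change.** State one threshold in Table 8 with its correct conversion: either 101°F [38.3°C] or 101.3°F [38.5°C]. The sponsor's clinical team should choose which value applies. Keeping 101°F makes the reduction compulsory at slightly lower temperatures; keeping 38.5°C raises the Fahrenheit cut-off by 0.3°F. A small rounding remainder is left if 38.3°C is chosen, since 38.3 × 9/5 + 32 = 100.94°F, but it is smaller than the 0.1°F step of a one-decimal reading.

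The cost is a correction to one figure. No analysis, sample size or data collection changes.

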6.8.2 Non-haematologic toxicity dose modifications

Substantial acute toxicities should be managed as medically indicated and with temporary suspension of investigational product, as appropriate. Dose reductions or holds and initiation of supportive care are allowed as clinically indicated by the treating physician.

Dose reductions of AZD1775 should be considered if the toxicity is considered to be related to AZD1775 (i.e., in monotherapy studies or in combination studies) if the relationship cannot be wholly attributed to the combination agent (each combination agent should be considered on an individual basis). Dose re-escalation is not permitted.

In general, if a patient experiences a Grade 1/Grade 2 non-haematological toxicity, no dose modification is required (except QTc prolongation; see table below). If a patient experiences a Grade 3 or Grade 4 toxicity which is not attributable to the disease or disease-related processes under investigation, dosing will be interrupted and/or the dose reduced, and supportive therapy administered as required. Any patient who develops a Grade 3 or 4 non-haematologic toxicity that does not resolve to \leq Grade 1 within 21 days should be removed from the study treatment unless approved by the Medical Monitor.

Table 9 AZD1775 dose modifications for QTc interval prolongation

Electrocardiogram QT corrected interval prolonged	
QTc Value	AZD1775
QTc 450-480 ms (males) or 470-480 (females)	Hold. Once QTc interval has returned to pretreatment status and correction of possible electrolyte imbalance has been made, resume at next lower dose level.
QTc 481-500 ms	Hold. Seek cardiologist advice.
QTc \geq 501 ms	Discontinue treatment
Shift from baseline of \geq 60ms	Discontinue treatment

6.8.3 Non-haematologic toxicity management guidelines

6.8.3.1 Diarrhoea

Due to frequent reports of diarrhoea with AZD1775 administration, vigorous anti-diarrhoeal treatment loperamide (Imodium) is required at the **first** onset of diarrhoea according to American Society of Clinical Oncology (ASCO) guidelines. Oral loperamide (Imodium) 4 mg should be administered at the first onset of diarrhea and then 2 mg every 2 hours until diarrhoea-free for at least 12 hours. The first dose of loperamide could be lowered to 2 mg if the diarrhoea is recurrent and if, in the opinion of the treating physician, the diarrhoea is not severe.

Patients should be instructed to notify the Investigator or research staff of the occurrence of bloody or black stools, symptoms of dehydration, fever, inability to take liquids by mouth, and inability to control diarrhoea within 24 hours of using loperamide or other prescribed anti-diarrhoeal medications.

If diarrhoea is severe (i.e., requiring intravenous [IV] rehydration) and/or associated with fever or severe neutropenia (Grade 3 or 4), broad-spectrum antibiotics must be prescribed. Patients with severe diarrhoea or any diarrhoea associated with severe nausea or vomiting should be hospitalised for IV hydration and correction of electrolyte imbalances.

6.8.3.2 Nausea and vomiting (mandatory anti-emetic prophylaxis)

All patients must receive a 5-HT3 antagonist, ondansetron (Zofran) 8 mg BID PO or granisetron (Kytril) 1 mg BID PO prior to each dose of AZD1775. Additional doses of 5-HT3 antagonist may be used if needed. In addition, dexamethasone 4 mg PO will be given with each AZD1775 dose as a minimum on the first day of dosing AZD1775 of every 3-5 days dosing period, unless contraindicated or not well-tolerated. Dexamethasone may be continued on further days of dosing, potentially at a lower dose. Dexamethasone or the 5-HT3 antagonist may be given by IV.

Promethazine (Phenergan), prochlorperazine (Compazine), and benzodiazepine may still be used as additional adjunctive treatments during AZD1775 therapy.

Please note: aprepitant [Emend] and fosaprepitant are not permitted due to known DDIs.

Patients should be strongly encouraged to maintain liberal oral fluid intake.

Suitable alternative medications may be used, with adequate justification, in those studies where the use of any of the above medications might interfere with other study procedures or deemed insufficient.

6.8.3.3 Febrile neutropenia

Patients experiencing febrile neutropenia with significant symptoms should be managed in a hospital setting according to standard procedures, with the urgent initiation of IV antibiotic therapy. Patients with febrile neutropenia without symptoms should be managed according to standard guidelines.

7. INVESTIGATIONAL PRODUCT AND OTHER TREATMENTS

7.1 Identity of investigational product(s)

AZD1775 is available as dry-filled capsules containing 25 or 100 mg of drug substance. Additional information about the investigational product (IP) may be found in the IB.

All study drugs must be kept in a secure place under appropriate storage conditions. The IP label on the bottle and the IB specifies the appropriate storage.

Investigational product	Dosage form and strength	Manufacturer
AZD1775	25 or 100 mg capsules	AstraZeneca

7.2 Dose and treatment regimens

AZD1775 will be taken by mouth in approximate 12 hour intervals over 3 days at the start of week 1 and 2 of each 21-day cycle (Days 1-3 and 8-10), for a total of 12 doses with each cycle (see [Figure 2](#)). Mandatory prophylactic anti-emetic therapy will be administered as described in Section [6.8.3.2](#).

AZD1775 should be taken with 8 ounces of water approximately 2 hours before and again 2 hours after food. If BID dosing and a patient misses one of the two daily doses according to schedule, the dose should be taken as soon as possible, but not more than 6 hours after the missed dose was scheduled. If greater than 6 hours, the missed dose should be skipped and the patient should take the next dose when scheduled.

[figure not shown]
If vomiting occurs after a patient takes the AZD1775 dose, the patient should be instructed not to retake the dose, but to wait until the next scheduled dose of AZD1775. If no dose is scheduled for the following day, the dose will not be 'made up'. If vomiting persists, the patient should contact the Investigator.

AZD1775 dosing compliance should be reviewed with the patient at the beginning of each new treatment cycle when study drug is dispensed. All patients will be required to complete a dosing diary, which must be returned to the clinic for review at each visit. The patient should be instructed to record each date and time the dose(s) were taken on the dosing diary. If a dose is missed, the reason must be noted in the diary. A copy of the dosing diary is provided in the study reference materials.

Patients should be advised to return any unused AZD1775 in the original bottles, in addition to returning any empty bottles.

Figure 2 **21-day cycle**
AZD1775 dosing schedule, 21-day cycle

Day of Cycle

7.2.1 Part A: Safety lead-in cohort (closed to enrolment – October 2015)

The safety and tolerability of AZD1775 monotherapy in patients with advanced solid tumours will be assessed in a safety lead-in cohort. Patients in the safety lead-in will receive the planned dose and schedule for the study, 200 mg PO BID for 3 days at the start of weeks 1 and 2 of each 21-day cycle. Pharmacokinetic and pharmacodynamics samples will be collected from all Part A patients (see Section 5.3.1). During the safety lead-in, the AZD1775 starting dose was reduced to 175 mg BID because 200 mg BID was not well-tolerated. Adverse events (AEs) associated with AZD1775, and DLTs observed during the safety lead-in included diarrhoea, vomiting and anaemia. In addition to reducing the starting dose of AZD1775, mandatory anti-emetic prophylaxis has been instituted (see Section 6.8.3.2). The Part A safety lead-in patient enrolment has been completed.

After approximately 12 evaluable patients have completed Cycle 1, a Safety Review Team (SRT [see Section 10.7]) will review the accumulated safety and tolerability data of the AZD1775 monotherapy dose and schedule. Patients must complete Cycle 1 safety evaluations which will conclude on Cycle 2 Day 1, and must receive at least 75% of the planned Cycle 1 dose to be considered evaluable. Patients receiving less than 75% of Cycle 1 dose will be replaced unless they experienced a confirmed DLT by the SRT.

At the end of Part A, if no safety signals are reported and the PK profile appears acceptable, the Part B tumour specific expansion cohorts will begin enrolment.

Dose-limiting toxicities thought to be related to the study drug during the safety lead-in phase will be defined as any of the following toxicities not attributable to the disease or disease-related processes under investigation, that occur from the first dose of study treatment up to the last day of Cycle 1 (first 21 days) and that meets at least 1 of the haematological or non-haematological criteria below:

1. Haematological toxicity \geq Grade 4 present for more than 7 days including:
 - Infection with febrile neutropenia
2. Grade 3 thrombocytopenia associated with Grade \geq 2 bleeding
3. Non-haematological toxicity \geq Grade 3
4. Grade \geq 3 total bilirubin, hepatic transaminase (alanine aminotransferase [ALT] or aspartate aminotransferase [AST]) or alkaline phosphatase (ALP) lasting $>$ 48 hours.
5. Changes in liver function tests (LFTs) consistent with the definition of Hy's Law (see Appendix C).
6. Any other toxicity that is clinically significant and/or unacceptable that does not respond to supportive care, results in a disruption of dosing schedule of more than

7 days, or is judged to be a DLT by the Investigator in collaboration with the Medical Monitor.

A DLT excludes:

- Alopecia of any grade
- Isolated laboratory changes of any grade without clinical sequelae or clinical significance

If appropriate the DLT observation period can be expanded by up to 2 weeks in case of treatment delay due to study drug-related adverse events. Treatment will be considered non-tolerated if 2 or more of the first 6 evaluable patients experience a DLT in the safety lead-in cohort. If the initial dose or schedule of the treatment is not tolerated, patient enrolment to the treatment will be stopped and either the schedule will be taken no further or the dose level or schedule of AZD1775 may be adjusted to evaluate safety in a second 6 patient cohort at the next lower dose level or revised schedule. The DLT criteria apply only to the safety lead-in patients during Cycle 1. Safety lead-in patients continuing treatment beyond Cycle 1 will have dose modifications applied according to Section 6.8.

If fewer than 2 out of the first 6 evaluable patients experience a DLT, enrolment will continue to approximately 12 evaluable patients to further evaluate safety. If 4 or more of 12 evaluable patients experience a DLT then the treatment will be considered not tolerated.

Investigators will be notified in a timely manner of any safety outcomes so that they may notify their Institutional Review Boards (IRBs).

